10.4 OBLIGATION OF THE INVESTIGATOR REGARDING SAFETY REPORTING

10.4.1 Definitions of adverse events

10.4.1.1 Adverse event

An **adverse event** (AE) is any untoward medical occurrence in a patient or clinical investigation patient administered a pharmaceutical product and which does not necessarily have to have a causal relationship with this treatment.

Intensity of an AE is defined as:

- Mild: no modification of daily activities and does not require mandatory corrective/symptomatic treatment.
- Moderate: hinders normal daily activities and/or requires mandatory corrective/symptomatic treatment.
- Severe: prevents daily activities and requires mandatory corrective/symptomatic treatment.

10.4.1.2 Serious adverse event

A **serious adverse event** (SAE) is any untoward medical occurrence that at any dose:

- Results in death, or,
- Is life-threatening, or,
Note: The term “life-threatening” in the definition of “serious” refers to an event in which the patient was at risk of death at the time of the event; it does not refer to an event which hypothetically might have caused death if it were more severe.
- Requires inpatient hospitalization or prolongation of existing hospitalization, or,
- Results in persistent or significant disability/incapacity, or,
- Is a congenital anomaly/birth defect.
- Is a medically important event.

Medical and scientific judgment should be exercised in deciding whether expedited reporting is appropriate in other situations, such as important medical events that may not be immediately life-threatening or result in death or hospitalization but may jeopardize the patient or may require medical or surgical intervention (ie, specific measures or corrective treatment) to prevent one of the other outcomes listed in the definition above.

Note: The following list of medically important events is intended to serve as a guideline for determining which condition has to be considered a medically important event. The list is not intended to be exhaustive:

- Intensive treatment in an emergency room or at home for:
 - Allergic bronchospasm,
 - Blood dyscrasias (ie, agranulocytosis, aplastic anemia, bone marrow aplasia, myelodysplasia, pancytopenia, etc),
 - Convulsions (seizures, epilepsy, epileptic fit, absence, etc).
- ALT >3 x ULN + total bilirubin >2 x ULN or asymptomatic ALT increase >5 x ULN.
- Syncope, loss of consciousness (except if documented as a consequence of blood sampling).
- Bullous cutaneous eruptions.

10.4.1.3 Adverse event of special interest

An adverse event of special interest (AESI) is an AE (serious or nonserious) of scientific and medical concern specific to the Sponsor's product or program, for which ongoing monitoring and immediate notification by the Investigator to the Sponsor is required. Such events may require further investigation in order to characterize and understand them. Adverse events of special interest may be added, modified or removed during a study by protocol amendment.

- Pregnancy of a female subject entered in a study as well as pregnancy occurring in a female partner of a male subject entered in a study with IMP:
 - Pregnancy occurring in a female patient entered in the clinical trial or in a female partner of a male patient entered in the clinical trial. It will be qualified as an SAE only if it fulfills one of the seriousness criteria (see [Section 10.4.1.2](#)),
 - In the event of pregnancy in a female participant, IMP should be discontinued,
 - Follow-up of the pregnancy in a female participant or in a female partner of a male participant is mandatory until the outcome has been determined.
- Symptomatic overdose (serious or nonserious) with IMP:
 - An overdose (accidental or intentional) with the IMP is an event suspected by the Investigator or spontaneously notified by the patient (not based on systematic pills count) and defined as at least twice the intended dose within the intended therapeutic interval, adjusted according to the tested drug.

Of note, asymptomatic overdose has to be reported as a standard AE.

- Increase in alanine transaminase (ALT)>3xULN (see [Appendix A](#) of the protocol).
- QTc \geq 500ms.
- Hypotension/orthostatic hypotension symptomatic or not defined as:
 - Asymptomatic orthostatic hypotension with SBP decrease at Minute 3 or Minute 5 between seated and standing position \geq 30 mmHg,
 - SBP <90 mmHg,
 - Symptomatic orthostatic hypotension with SBP decrease at Minute 3 or Minute 5 between seated and standing position \geq 20 mmHg,
 - Symptoms of hypotension (either orthostatic or non-postural) include: presyncope, including any symptoms of dizziness, faintness or lightheadedness appearing while standing up and possibly caused by a drop in BP and/or appearing while standing up,
 - Whenever possible, concomitant medications, BP and heart rate measurements in seated and standing positions, plasma glucose level and ECG will be collected at or near the time of the event or per the investigator's clinical judgment,
 - For any such event, the appropriate AESI eCRF screen must be filled out.

Note: the following non-pharmacological measures will be encouraged by discussing with the patient: If a patient experiences faint-headedness or unusual dizziness, he or she will assume a seated position and, if still dizzy, either lie down or, while seated, place the head between the knees until dizziness has passed; the patient will be recommended to drink at least 12 ounces (375 mL) of fluid.

10.4.2 Serious adverse events waived from expedited regulatory reporting to regulatory authorities

Not applicable.

10.4.3 General guidelines for reporting adverse events

- All AEs, regardless of seriousness or relationship to IMP/NIMP, spanning from the signature of the informed consent form until the end of the study as defined by the protocol for that patient, are to be recorded on the corresponding page(s) or screen(s) of the eCRF:
 - Whenever possible, diagnosis or single syndrome should be reported instead of symptoms. The Investigator should specify the date of onset, intensity, action taken with respect to IMP, corrective treatment/therapy given, additional investigations performed, outcome, and his/her opinion as to whether there is a reasonable possibility that the AE was caused by the IMP/NIMP or by the study procedure(s),
 - The Investigator should take appropriate measures to follow all AEs until clinical recovery is complete and laboratory results have returned to normal, or until progression has been stabilized, or until death, in order to ensure the safety of the patients. This may imply that observations will continue beyond the last planned visit per protocol, and that additional investigations may be requested by the monitoring team up to as noticed by the Sponsor. Patients who experience an ongoing SAE or an AESI, at the prespecified study end-date, should be followed until resolution, stabilization, or death and related data will be collected,
 - When treatment is prematurely discontinued, the patient's observations will continue until the end of the study as defined by the protocol for that patient,
 - Laboratory, vital signs or ECG abnormalities are to be recorded as AEs only if:
 - Symptomatic and/or,
 - Requiring either corrective treatment or consultation, and/or,
 - Leading to IMP discontinuation or modification of dosing, and/or,
 - Fulfilling a seriousness criterion, and/or,
 - Defined as an AESI.

Instructions for AE reporting are summarized in [Table 5](#).

10.4.4 Instructions for reporting serious adverse events

In the case of occurrence of an SAE, the Investigator or any designees must immediately:

- ENTER (within 24 hours) the information related to the SAE in the appropriate screens of the e-CRF; the system will automatically send a notification to the monitoring team after approval of the Investigator within the e-CRF or after a standard delay.

- SEND (preferably by fax or e-mail) a photocopy of all examinations carried out and the dates on which these examinations were performed, to the representative of the monitoring team whose name, fax number, and email address appear on the clinical trial protocol. Care should be taken to ensure that the patient's identity is protected and the patient's identifiers in the clinical trial are properly mentioned on any copy of a source document provided to the Sponsor. For laboratory results, include the laboratory normal ranges.
- All further data updates should be recorded in the e-CRF as appropriate, and further documentation as well as additional information (for laboratory data, concomitant medications, patient status, etc) should be sent (by fax or e-mail) to the monitoring team within 24 hours of knowledge of the SAE. In addition, every effort should be made to further document any SAE that is fatal or life-threatening within a week (7 days) of the initial notification.
- A back-up plan (using a paper CRF process) is available and should be used when the e-CRF system does not work.

Any SAE brought to the attention of the Investigator at any time after the end of the study for the patient and considered by him/her to be caused by the IMP with a reasonable possibility, should be reported to the monitoring team.

10.4.5 Guidelines for reporting adverse events of special interest

For AESIs, the Sponsor must be informed immediately (ie, within 24 hours), as per SAE notification guidelines described in [Section 10.4.4](#), even if not fulfilling a seriousness criterion, using the corresponding pages of the CRF (to be sent) or screens in the e-CRF. Instructions for AE reporting are summarized in [Table 5](#).

10.4.6 Guidelines for management of specific laboratory abnormalities

Decision trees for the management of certain laboratory abnormalities by Sanofi are provided in [Appendix A](#).

The following laboratory abnormalities should be monitored, documented, and managed according to the related flow chart in protocol appendices.

- Neutropenia.
- Thrombocytopenia.
- ALT increase.
- Acute renal insufficiency.
- Suspicion of rhabdomyolysis.

Table 5 - Summary of adverse event reporting instructions

Event category	Reporting timeframe	Specific events in this category	Case Report Form completion		
			AE form	Safety Complementary Form	Other specific forms
Adverse Event (non-SAE, non-AESI)	Routine	Any AE that is not SAE or AESI	Yes	No	No
Serious Adverse Event (non-AESI or AESI)	Expedited (within 24 hours)	Any AE meeting seriousness criterion per Section 10.4.1.2	Yes	Yes	No
Adverse Event of Special Interest	Expedited (within 24 hours)	Pregnancy	Yes	Yes	Yes
		Symptomatic overdose with IMP	Yes	Yes	No
		ALT increase as defined in the protocol	Yes	Yes	Yes
		QTc \geq 500ms	Yes	Yes	No
		Hypotension/orthostatic hypotension (asymptomatic and symptomatic)	Yes	Yes	No

10.5 OBLIGATIONS OF THE SPONSOR

During the course of the study, the Sponsor will report in an expedited manner:

- All SAEs that are both unexpected and at least reasonably related to the IMP (SUSAR), to the regulatory authorities, independent ethics committee (IECs)/institutional review boards (IRBs) as appropriate and to the Investigators.
- All SAEs that are expected and at least reasonably related to the IMPs to the regulatory authorities, according to local regulations.

Adverse events that are considered expected will be specified by the investigator's brochure.

Any other AE not listed as an expected event in the Investigator's Brochure or in this protocol will be considered unexpected.

For regulatory purposes, the treatment code will be unblinded at Sponsor Pharmacovigilance department level for reporting to the Health Authorities of any suspected unexpected adverse drug reaction (SUSAR) and reasonably associated with the use of the IMP according to either the judgment of the Investigator and/or the Sponsor. Apart from Sponsor Pharmacovigilance department, within the company and associated organizations, the results of this unblinding will remain undisclosed.

The Sponsor will report all safety observations made during the conduct of the trial in the clinical study report.

10.6 SAFETY INSTRUCTIONS

In case of signs or symptoms suggestive of hypotension or orthostatic hypotension occur, physical examinations will include respiratory, cardiovascular systems; clinical management of this hypotension should be undertaken by the investigator. If the event persisted, decision of IMP discontinuation should be discussed with the Sponsor.

10.7 ADVERSE EVENTS MONITORING

All events will be managed and reported in compliance with all applicable regulations, and included in the final clinical study report.

11 STATISTICAL CONSIDERATIONS

11.1 DETERMINATION OF SAMPLE SIZE

The sample size calculations are based on the primary efficacy variable of uncorrected global CFR assessed by ¹³N-ammonia or ⁸²Rubidium PET scan change from baseline to Week 4.

Assumptions for sample size calculation:

- A large study of 2783 patients referred for rest/stress positron emission tomography suggested a SD 0.65 for CFR at baseline. With the hypothesis of correlation of 0.6 between baseline assessment and Week 4 assessment the SD for the change of baseline to week for could be estimated at 0.58
- A t-test at a 1-sided 5% significance level.

Based on the above assumptions, 35 evaluable patients per arm are needed for this study to detect a treatment effect of 0.35 with 80% of power. 10% more patients will be randomized in each group. Thus, approximately 78 patients will be randomized in this study, 39 per arm.

Calculations were made using East 6.3.

11.2 DISPOSITION OF PATIENTS

Screened patients are defined as any patient who originally met the inclusion criteria and signed the informed consent.

Randomized patients consist of all screened patients with a double-blind treatment kit number allocated and recorded in the IVRS/IWRS database, regardless of whether the treatment kit was used or not.

Patients treated without being randomized will not be considered as randomized and will not be included in any efficacy population. The safety experience of patients treated and not randomized will be reported separately, and these patients will not be in the safety population.

For any patient randomized more than once, only the data associated with the first randomization will be used in any analysis population. The safety experience associated with any later randomization will be assessed separately.

11.3 ANALYSIS POPULATIONS

11.3.1 Efficacy populations

11.3.1.1 Modified intent-to-treat population

The primary population for analysis will be the modified ITT (mITT) population: all randomized patients analyzed according to the treatment group allocated by randomization, who received at least a dose or part of a dose of the IMP and with an evaluable primary efficacy endpoint. The primary efficacy endpoint will be considered evaluable when the baseline CFR assessment is available.

11.3.2 Safety population

The safety population will be the as-treated population, defined as randomized population who did actually receive at least one dose or part of a dose of IMP and analyzed according to the treatment actually received.

In addition:

- Randomized patients for whom it is unclear whether they took the study medication will be included in the safety population as randomized.
- For patients receiving more than 1 study treatment during the trial, the treatment group allocation for as-treated analysis will be the active group if at least one active dose or part of a dose was taken.

11.3.3 Pharmacokinetic and biomarker analysis population

The population for all PK analyses will be all randomized and treated patients (safety population) having at least one sample.

The population for BM analysis will be randomized and treated patients from selected sites having at least a baseline and a post-baseline biomarker assessment.

11.4 STATISTICAL METHODS

11.4.1 Extent of study treatment exposure and compliance

11.4.1.1 Extent of investigational medicinal product exposure

Duration of IMP exposure is defined as: last dose date – first dose date +1 day, regardless of unplanned intermittent discontinuations.

11.4.1.2 Compliance

A given administration will be considered noncompliant if the patient did not take the planned dose of treatment as required by the protocol. No imputation will be made for patients with missing or incomplete data.

Treatment compliance, above-planned and under-planned dosing percentages will be summarized descriptively (N, mean, SD, median, min, and max). The percentage of patients with compliance <80% will be summarized. In addition, the number and percentage of patients with at least 1 above-planned dosing administration will be given, as well as the number and percentage of patients with 0, (0, 20%], and >20% under-planned dosing administrations.

11.4.2 Analyses of efficacy endpoints

11.4.2.1 Analysis of primary efficacy endpoint

Model assumptions for normality will be explored prior to the analysis testing.

Assuming that the change in CFR from baseline to Week 4 distribution is normal, an analysis of covariance (ANCOVA) model including the two following fixed categorical effect: treatment group (pooled SAR407899 doses versus placebo) and the presence of angiographically successful PCI (YES/NO) as well as a continuous fixed covariate of baseline CFR will be fitted. The interaction factors will be explored. The final model will provide adjusted least-squares means (LS means) estimates of the change from baseline to Week 4 in both treatment groups with their corresponding 95% confidence intervals (CIs). The difference of these estimates will be tested at the 1-sided 5% level using an appropriate contrast statement and the 95% confidence interval of the difference will be provided.

Let μ_0 and μ_1 be the population means of the change from baseline to Week 4 in CFR under placebo and SAR407899, respectively. The null hypothesis that will be tested is:

$H_0: \mu_0 = \mu_1$ versus $H_1: \mu_0 \neq \mu_1$.

Robustness of this statistical method will be assessed via sensitivity analyses detailed in the Statistical Analysis Plan (SAP), including different methodologies for missing data (multiple imputation and potentially pattern mixture modeling).

In this primary analysis, the mITT population is considered and the Week 4 assessments will be used regardless of whether the patient has previously discontinued the treatment.

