
STATISTICAL CONSIDERATIONS
	
Sample size determination:
 
Estimated as 78 patients (39 per group). Based on a large study of 2783 patients referred for rest/stress PET (1) which suggested a SD of 0.65 for CFR at baseline. Under the hypothesis of a correlation of 0.6 between baseline assessment and week 4-assessment the SD for the change from baseline to Week 4 could be estimated at 0.58.
 
35 patients per group will be needed to detect with 1 sided test alpha 0.05 and 80% power, a clinically significant relevant difference versus placebo of 0.35 in the change from baseline in PET CFR to Week 4.
 
To reach this number of patients 78 patients need to be included in this study with the hypothesis of 10% inevaluable.
 
Analysis population:
 
The efficacy population will be the modified intend-to-treat population, defined as all randomized patients analyzed according to the treatment group allocated by randomization, receiving at least one dose or part of a dose of the investigational medicinal product and having a baseline PET scan CFR assessment available.
 
The safety population will include all randomized patients who received at least one dose or part of a dose of the IMP. In the safety analysis, patients will be analyzed in the treatment group as actually received.
 
Primary analysis: efficacy analyses will be performed on ITT population.
 
The change in CFR from baseline to week 4 will be analyzed using an ANCOVA model. The model will include the two fixed categorical effect of treatment group (pooled SAR407899 doses versus placebo) and of the presence of angiographically successful PCI (YES/NO) as well as a continuous fixed covariate of baseline CFR. The corresponding interaction of order two will be also included in the model.
 
The final model will provide adjusted least-squares means (LS means)

	
estimates of the change from baseline to Week 4 in both treatment groups and their corresponding 95% confidence intervals. The difference of these estimates will be tested at the 5% 1-sided alpha level and the 95% confidence interval of the difference will be provided.
 
To evaluate the impact of missing values on treatment effect estimation, a multiple imputation method will be used.

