	
Analysis of the key secondary endpoint:
 
The secondary analysis will use a similar model as primary analysis applied to the change from baseline to Week 4 in SAQ PL. The final model will provide adjusted least-squares means (LS means) estimates of the change from baseline to Week 4 in both treatment groups and their corresponding 95% confidence intervals. The difference of these estimates will be tested at the 10% 1-sided alpha level and the 95% confidence interval of the difference will be provided.
 
A safety review with a DMC meeting will start as soon as the first 19 patients will have been randomized and have finished the first week of treatment. Additional analyses for safety may be performed in this study.
 
Safety analysis:
 
Safety analyses will be descriptive, based on the safety population with a focus on BP, creatinine and cystatin C.
 
The safety analysis will focus on the TEAE period. This period is defined as the time from the first administration of the IMP to the last administration of the IMP +5 times the half-life. The half-life being from 20 to 31 hours depending on the age of the patients, a conservative estimate of 31 hours is used for all patients (thus 5 times the half-life corresponds to 5 times 31 hours ie, approximately 7 days).
 
Pharmacokinetic analysis:
 
Descriptive statistics will be provided by SAR407899 dose and time-point for observed concentrations.
 
Pharmacokinetic/pharmacodynamic analysis:
 
Scatter plots of concentrations versus primary/secondary endpoints will be provided. If relevant, some models will be provided to fit the relationship between concentrations and endpoint(s).

DURATION OF STUDY PERIOD (per patient)
	
 • Screening: up to 4 weeks before the first dosing (Day -28 to Day -1) and up to 6 weeks in patients diagnosed with MVA and stable angina without previous PCI who did not have a coronary artery angiography or CCTA in the previous 24 months but between 24 months and 5 years prior to screening and requiring CCTA in this screening period. • Titration phase: 3 weeks. • Maintenance phase: 1 week. • Total duration of treatment: 4 weeks (including titration). • Follow-up: 1 week. • Total study duration: 9 weeks (+/- 2 days) and up to 11 weeks (+/- 2 days) in patients requiring CCTA in screening period.

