11.4.2.2 Analyses of secondary efficacy endpoints

The score of the SAQ-Physical Limitation scale will be derived according to the SAQ scoring instructions.

Assuming that the change from baseline to Week 4 in SAQ-Physical Limitation score distribution is normal, a similar model as primary analysis will be fitted. The interaction factors will be explored. The final model will provide adjusted least-squares means (LS means) estimates of the change from baseline to Week 4 in both treatment groups with their corresponding 95% confidence intervals (CIs). The difference of these estimates will be tested at the 1-sided 10% level using an appropriate contrast statement and the 95% confidence interval of the difference will be provided.

In this analysis, the mITT population is considered and the Week 4 assessments will be used regardless of whether the patient has previously discontinued the treatment.

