11.4.2.3 Multiplicity considerations

Results of secondary analysis are considered informative ONLY if the primary analysis is positive, therefore the study overall type I error does not need to be adjusted for multiplicity.

For secondary and exploratory efficacy endpoints, p-values will be provided for descriptive purpose only.

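### Does the two-sided alternative beside a one-sided 5% test of CFR, reported with a 95% interval, leave the primary decision rule unclear?

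*Protocol*

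**What the plan says.** **Primary endpoint.** Protocol 11.4.2.1 compares the adjusted mean changes in CFR from the ANCOVA; the difference is "tested at the 1-sided 5% level using an appropriate contrast statement and the 95% confidence interval of the difference will be provided". The hypotheses follow, introduced by "The null hypothesis that will be tested is": equality of the two population means, against an alternative that they are unequal. No direction is written.

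**Other statements of the primary test.** The synopsis sizes the trial with "35 patients per group will be needed to detect with 1 sided test alpha 0.05 and 80% power" and says of the analysis: "The difference of these estimates will be tested at the 5% 1-sided alpha level". Section 11.1 lists among its assumptions "A t-test at a 1-sided 5% significance level".

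**SAQ-PL.** For this endpoint, which it calls the key secondary, the synopsis says: "The difference of these estimates will be tested at the 10% 1-sided alpha level". Section 11.4.2.2 repeats the level: "The difference of these estimates will be tested at the 1-sided 10% level". Both promise a 95% interval. Section 11.4.2.3 first makes secondary results informative only when the primary analysis is positive, and then adds: "For secondary and exploratory efficacy endpoints, p-values will be provided for descriptive purpose only".

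**SAP.** Section 1.2 reports early termination with 10 patients randomized, 8 of them with a post-baseline CFR, and withdraws formal analysis. Table 1 replaces 11.4.2.1 and 11.4.2.2 with descriptive tables and listings without models, and marks 11.4.2.3 as not applicable.

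**The concern.** Three things look wrong.

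1. A one-sided test and a non-directional alternative do not describe the same test. Someone who worked from the hypotheses alone could run a two-sided 5% test, which is stricter and has less power at the planned size.
2. A one-sided 5% test corresponds to a 90% two-sided interval or a one-sided 95% lower bound. Only a 95% interval is planned for the difference, so a report could show a successful test beside an interval that includes zero.
3. SAQ-PL has a significance level, a condition on the primary result and a descriptive label. The plan does not say what meeting the 10% level would allow anyone to claim.

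At stake would be the clarity of the primary decision, and the risk that SAQ-PL is presented as confirmed when it was meant as description.

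**Working it through.** **Inputs.** From the protocol synopsis and section 11.1: baseline SD of CFR 0.65; correlation of baseline with Week 4 0.6; SD of change 0.58; difference 0.35; power 80%; one-sided 5% t-test; 35 evaluable per arm; 10% inevaluable; 78 randomized.

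**Step 1: reproduce the plan's figures.**
- SD of change = 0.65 × √(2 × (1 − 0.6)) = 0.581, stated as 0.58.
- Standard error of the difference with 35 per arm = 0.58 × √(2/35) = 0.1386, with 68 degrees of freedom.
- One-sided 5%, noncentral t: power at 0.35 is 80.4%, and 35 is the smallest number per arm that reaches 80%.
- Allowance for inevaluable patients: 35 / 0.9 = 38.9, so 39 per arm and 78 in total, as stated.

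**Step 2: try the alternative as written.** A two-sided 5% test with 35 per arm has 70.1% power and needs 45 per arm for 80% (44 by the normal approximation). It does not give 35. The non-directional alternative is therefore the part out of line, and the sample size is consistent with the test as described.

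**Step 3: compare the test with the 95% interval (35 per arm, SD 0.58).**

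| Quantity | One-sided 5% test | 95% interval excludes zero |
|---|---|---|
| Critical t, 68 df | 1.668 | 1.995 |
| Observed difference needed | 1.668 × 0.1386 = 0.231 | 1.995 × 0.1386 = 0.277 |
| Probability if the true difference is 0.35 | 80.4% | 70.1% |

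A result falls between the two cut-offs in 80.4% − 70.1%, about 10.2% before rounding, of trials with a true difference of 0.35. With no true difference the share is 5% − 2.5% = 2.5%.

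Example: an observed difference of 0.25 gives t = 0.25 / 0.1386 = 1.803 and one-sided p = 0.038. The 95% interval is 0.25 ± 0.277, or −0.027 to 0.527; the 90% interval is 0.25 ± 0.231, or 0.019 to 0.481.

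**Step 4: the same comparison for an ANCOVA.** Assume equal variances at both visits, correlation 0.6 and no interaction terms. The last is a simplification: the synopsis includes the interaction in the model, while 11.4.2.1 only explores it. Residual SD = 0.65 × √(1 − 0.36) = 0.52; standard error = 0.52 × √(2/35) = 0.1243; 66 degrees of freedom. The cut-offs are 0.207 and 0.248, the share between them is 8.1%, and one-sided power is 87.3%.

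**Step 5: what the figures measure.** Steps 3 and 4 measure the gap between the test and a 95% interval. They do not measure an effect of the hypothesis wording: an analyst who follows the four one-sided statements uses the same test, with the same sample size and power, whichever way the alternative is written.

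**The case for a change.** The strongest case for a correction is that the hypotheses belong to the primary decision rule and should agree with the test. Without a direction, section 11.4.2.1 does not say in symbols that success means a higher CFR on SAR407899. SAP section 1.1 still points to protocol section 11 as the full account of the statistical strategy, and SAP Table 1 does not mention the hypotheses. The inconsistency stays on record and could be copied into a later protocol. For SAQ-PL, a condition on the primary result suggests inference while the descriptive label denies it. The correction would cost only words.

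The textual observations stand: the alternative should have been directional, and the three statements on SAQ-PL do not fit together neatly. The consequences do not follow. Section 4.3 gives the direction, since the study asks whether the drug improves CFR, and the sample size targets a difference versus placebo of 0.35. Four statements fix the one-sided level, and the planned numbers confirm it.

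On the interval, the decision rule is the test and the interval serves estimation. A wider interval than the test requires does not flatter the drug. A 90% interval would be a helpful extra, but leaving it out breaks no rule in the plan.

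On SAQ-PL, the condition in 11.4.2.3 already limits how the result may be read, and the descriptive label prevents a confirmatory claim. The 10% level is then a benchmark with no claim attached.

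On the SAP, section 1.2 lists the replacements after section 1.1 gives the background reference. Those replacements cover all three protocol subsections concerned.

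**Conclusion.** No change is needed. The non-directional alternative in 11.4.2.1 is a clerical slip; the rest of the plan settles the test as one-sided 5%. Correcting it would leave 35 evaluable per arm, 78 randomized and 80.4% power as they are.

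The 95% interval is a fair reporting choice. Its largest practical effect would have been an 8% to 10% chance, if the true difference were 0.35, of a successful test shown beside an interval that includes zero. That range rests on the plan's SD and correlation, 35 evaluable per arm, the usual two-sided reading of a 95% interval and, for the lower figure, an ANCOVA without interactions. A reader given the one-sided p-value could interpret such a result correctly.

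The SAQ-PL wording is untidy, but its p-value is descriptive and is read only after a positive primary result.

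All of this is now hypothetical. With 10 of 78 planned patients randomized, the SAP fits no model and performs no test, so rewording would alter neither an output nor a conclusion.
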